Research Question/Aim(s)	
Primary aims
 
 • To identify the infections leading to death in babies on UK neonatal units. • To define the clinical characteristics of babies dying from infections. • To describe the management of babies dying from infections with a specific focus on their antimicrobial treatment and the antimicrobial resistance profiles of the causative organisms.
	
Secondary aims
 
In a case-control study to assess the hypothesis that babies who die from bacterial infections on neonatal units do so because they receive inappropriate antibiotic management.
 
To do this, babies who die from confirmed bacterial infections will be compared with babies who survive bacterial infections on a range of factors including appropriateness, dose and timeliness of antibiotic use.

FUNDING AND SUPPORT	
FUNDER(S)	FINANCIAL AND NON FINANCIAL SUPPORT GIVEN
Antibiotic Research UK (ANTRUK)	£4,000 over 36 months

ROLES AND RESPONSIBILITIES OF STUDY MANAGEMENT COMMITTEES/GROUPS & INDIVIDUALS

PROTOCOL CONTRIBUTORS

[name] and [name] (St. George's University of London) conceived the study; [name] and [name] initiated the study design and helped with implementation and will conduct primary statistical analysis. St. George's, University of London is the grant holder. All authors contributed to refinement of the study protocol and will approve the final manuscript.

STUDY TIMELINE

Key Objective	Measure of objective	Objective end point date
Application for modification of ethics permission for neonIN database	ethics approval	June 2018
Adaptation of on-line neonIN database	neonIN database adapted for new data	June 2018
Meeting of neonIN teams	meeting	July 2019
Set up of neoAMRO sites	preparation to start data collection	August 2019
On-line data collection commences	data entries	August 2019
Formal review of neonIN/neoAMRO data collection progress at 30 months	completeness of data, number of deaths recorded (>10)	February 2022
Formal review of neonIN/neoAMRO data collection at 36 months	completeness of data, number of deaths recorded (>40)	August 2022
neonIN /neoAMRO data collection completed at 49 months	completion of data entry	September 2023
analysis of all data and study report	study report completion	February 2024

ABBREVIATIONS	
AE	Adverse Event
AR	Adverse Reaction
BSI	Blood Stream Infection
CI	Chief Investigator
CRF	Case Report Form
GCP	Good Clinical Practice
GP	General Practitioner
GNB	Gram-Negative Bacteria

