1 BACKGROUND

In 2011 we undertook a detailed analysis of death certificates over a 3 year period (England and Wales) and identified infection as the cause of 11% of neonatal deaths [1]. Where a pathogen was identified, 81% were bacterial, 11% were fungal and 9% were viral. The presentation of neonatal infection is non-specific therefore antimicrobial treatment is commenced before a causative organism is identified (called empiric therapy). The antimicrobial resistance patterns of the bacteria causing infections in our neonatal infection surveillance network (neonIN) show that there is a mismatch between recommended empiric antibiotics and the susceptibilities of relevant pathogens in a significant proportion (5-16%) [2,3]. The implication of these findings is that when the “wrong” empiric antibiotic combination is used to treat an infection the infant will be untreated until this is recognised and this may lead to a poor outcome, including death. For example, in a recent neonIN analysis of 118 episodes of Gram-negative neonatal infection, the 10 day attributable mortality was 18%, but this increased to 100% in those with strains resistant to gentamicin (a commonly used antibiotics in empiric regimens) (3/3) [4].

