4.2 Secondary aim

- In a case-control study we will assess the hypothesis that babies who die from bacterial infections on neonatal units do so because they receive inappropriate antibiotic management. To do this we will compare babies who die from bacterial infections with babies who survive bacterial infections on a range of factors including appropriateness, dose and timeliness of antibiotic use.

5 STUDY DESIGN and METHODS of DATA COLLECTION and DATA MANAGEMENT

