7.2 Sampling

7.2.1 Size of sample

Based on our previous data collection (see ref. 2), at the end of the enhanced study period we would expect to have data on up to 800 babies with invasive neonatal infections, approximately 50% will be due to coagulase negative staphylococci (CoNS), approximately 25% will be early onset sepsis and approximately 200 will be Gram-negative sepsis. Based on our recent data for case fatality rates (18% for Gram-negative bacteraemia, 8% for Group B streptococcus, 5% for staphylococcal aureus), we would expect around 50 deaths in this cohort.

All babies who have died within 28 days of a positive culture will then be compared with babies who have survived at 28 days across a range of relevant clinical and demographic factors. For all cases and for two controls per case (selected centrally, based on birth in same birthweight category and in same hospital), this will be performed through collection of anonymised data including birth gestation, birth weight and age at infection, antimicrobials administered for that infection episode (and if changed), relapses, length of stay and attributable mortality at 10 days using a standardised case report form. With approximately 50 cases of death and 100 controls, we anticipate that we will be able to explore the relationship between initial antimicrobial therapy and isolate susceptibility, with outcome, with great certainty. For example, with this sample size we can demonstrate a difference between susceptibility to empiric antibiotics of 80% among cases (or less) to 95% among controls, with 95% significance and 80% power; a difference that is clinically meaningful. A 10-day cut-off for attributable mortality will be used as early mortality is assumed to be more likely a direct consequence of infection than late mortality. Other risk factors for death will be assessed in univariate and multivariable logistic regression analyses.

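### Section 7.2.1 takes every death within 28 days of any positive culture as a case, but the secondary aim concerns death from bacterial infection

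*Protocol*

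**What the plan says.** The Protocol describes the case group in these places.

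- Study summary, secondary aims: "babies who die from confirmed bacterial infections will be compared with babies who survive bacterial infections". Section 4.2 says the same: "we will compare babies who die from bacterial infections with babies who survive bacterial infections". Here a case is defined by cause and by type of organism, with no time window.
- Section 7.2.1: "All babies who have died within 28 days of a positive culture will then be compared with babies who have survived at 28 days". Here a case is defined by a time window alone. Two controls per case are then selected centrally, by hospital and birthweight category.
- Section 7.2.1, same paragraph: "A 10-day cut-off for attributable mortality will be used as early mortality is assumed to be more likely a direct consequence of infection". Attributable mortality at 10 days is also among the items collected on the case report form.
- Section 7.1 admits any infant on a participating unit with an episode of culture-positive infection, without exceptions and without an organism restriction.
- Sections 5.2, 5.3 and 8.6 record whether infection was associated with the death. No section uses that field to select cases.

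On size, section 7.2.1 expects around 50 deaths, from fatality rates of 18% (Gram-negative), 8% (Group B streptococcus) and 5% (Staphylococcus aureus). It claims 80% power with 50 cases and 100 controls for susceptibility to empiric antibiotics of 80% versus 95%. Section 1 reports, for Gram-negative episodes, that "the 10 day attributable mortality was 18" per cent.

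**The concern.** A baby who dies on day 25 of an unrelated condition, after a cleared bacteraemia, is a case under section 7.2.1 and not under section 4.2. So is a baby who dies of a fungal infection. Because controls are drawn to match the cases, the case definition decides who enters both groups.

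Two things are at stake. First, the estimate: deaths unrelated to the infection should resemble survivors in how well the empiric antibiotics covered the isolate, so including them weakens the contrast the aim is about. Second, the planning: the expected number of deaths appears to be projected on one kind of death and the cases sampled on another. With the definition unsettled, the result can also depend on which case set is reported.

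**Working it through.** **Inputs.** From section 7.2.1: 50 cases, 100 controls, susceptibility 80% versus 95%, 5% significance (taken as two-sided), 80% power, about 200 Gram-negative episodes among up to 800, half of the 800 being coagulase-negative staphylococci. Assumed, because the documents give no figure: the share f of 28-day deaths not caused by the infection, shown for 10%, 20% and 30%, and that such deaths have the controls' 95% susceptibility.

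**The plan's own power.** Two-proportion formula with pooled variance under the null:

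- pooled proportion = (50 × 0.80 + 100 × 0.95)/150 = 0.90
- SE under the null = √[0.90 × 0.10 × (1/50 + 1/100)] = 0.0520
- SE under the alternative = √[0.80 × 0.20/50 + 0.95 × 0.05/100] = 0.0606
- z = (0.15 − 1.96 × 0.0520)/0.0606 = 0.79, so power = 78.7%

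Eighty per cent power needs 52 cases at 1:2. The stated figure reproduces, provided every case carries the full contrast.

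**Where the 50 deaths come from.** Gram-negative: 200 × 0.18 = 36. Episodes that are neither Gram-negative nor coagulase-negative staphylococci: 800 − 400 − 200 = 200. If these carry 5% to 8% (assumed to apply to all of them), they add 10 to 16 deaths, for a total of 46 to 52. So around 50 can be reached from bacterial rates alone. The 18% matches the 10-day attributable rate in section 1; that it is the same figure is an inference from the match.

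**Effect of unrelated deaths.** Case susceptibility = 0.80(1 − f) + 0.95f. Two readings of the 50 are possible: (a) the 50 are all 28-day deaths; (b) the 50 are infection deaths and the others come on top, giving 50/(1 − f) cases. Both keep two controls per case.

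| f | Susceptible, cases | Odds ratio for non-susceptibility | Power, (a) 50 cases | Power, (b) |
|---|---|---|---|---|
| 0 | 80.0% | 4.75 | 78.7% | 78.7% (50 cases) |
| 10% | 81.5% | 4.31 | 72.6% | 76.8% (56 cases) |
| 20% | 83.0% | 3.89 | 65.5% | 73.7% (62 cases) |
| 30% | 84.5% | 3.49 | 57.4% | 70.8% (71 cases) |

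**Restricting the cases instead.** If the 50 are all 28-day deaths and only infection deaths are kept, still at 80% versus 95% and 1:2, then 45, 40 and 35 cases give 74.8%, 70.3% and 65.2% power. Compared with (a), that recovers about 2, 5 and 8 points. It does not restore 79%.

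**Fungal deaths.** Section 1 gives, for infection deaths on death certificates: "Where a pathogen was identified, 81% were bacterial, 11% were fungal and 9% were viral". Taking 11% as an illustration, about 5.5 of 50 cases would be fungal. Dropped from the susceptibility comparison, they leave 44.5 cases and 74.4% power. Counted as non-susceptible, they lower case susceptibility to 0.80 × 0.89 = 71.2% and widen the difference from 15 to 23.8 points, an artefact of coding.

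**The case against.** The strongest reply is that the definitions nest: sample all 28-day deaths, record the association with infection, then examine attributable deaths up to day 10. How the recorded field is used could be left to a statistical analysis plan, which is not shown. The case-control study is also only a secondary aim, and the primary descriptive aims are unaffected.

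Part of this stands. A reader might infer three rival case definitions, but the documents do not show that. Ten-day attributable mortality is listed as a collected item, so "A 10-day cut-off for attributable mortality will be used" may describe a separate outcome; its role is simply not stated. The firm conflict is between two definitions, in sections 4.2 and 7.2.1. That conflict does not go away, because the Protocol itself fixes both and selects controls from one of them.

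A reader might also infer that fungal deaths dilute the comparison. They need not: the direction depends on how they are counted. The 11% comes from death certificates, not from this cohort.

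Finally, section 7.2.1 gives 80% or less among cases, as an example, directly after making 28-day deaths the cases, so the 80% might already include unrelated deaths. In that event the stated power stands, but for a contrast other than the one in the aim.

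**Conclusion.** The conflict is in the current text: following section 7.2.1 yields a case group that does not answer section 4.2. The size of the harm cannot be derived from the documents. Under an assumed unrelated share of 10% to 30%, power is 73% to 57% if the 50 are all 28-day deaths, and 77% to 71% if unrelated deaths come on top.

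It would be tempting to report only the steeper loss. That is not supported: if the 50 rest mainly on a 10-day attributable rate, as 36 of them seem to, other deaths would be added to the 50 and the milder range applies. Both ranges assume that 80% is the value among infection deaths and that unrelated deaths look like controls. Under either reading there is no slack, since the plan starts at 78.7%.

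**What to change.** In section 7.2.1:

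1. Restrict case-control cases and controls to bacterial isolates. Fungal and other deaths stay in the descriptive primary aims.
2. State one primary case definition that matches section 4.2: death within 28 days of the positive culture, recorded as associated with the bacterial infection. Controls are survivors of bacterial infection at 28 days.
3. Name two sensitivity analyses: all-cause 28-day death, and death within 10 days counted from the dates. They are needed because the local team that judges the association also knows the antibiogram and the treatment given. State that this is the role of the 10-day cut-off.
4. Re-project the number of cases and the power on the chosen definition, saying which kind of death each fatality rate counts.

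The change is one of wording: isolates, dates of death and the association field are already collected. The cost is that some 28-day deaths leave the primary case set, by a number the documents do not give, so the stated 80% power may have to be lowered. Making all-cause 10-day death primary would not be a better match: it keeps early deaths from other causes and loses infection deaths on days 11 to 28.

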5.3 Data collection

Invasive infection episodes will be captured prospectively on a web-based infection surveillance database called neonIN (www.neonin.org.uk) which is coordinated by [name] at St George's University of London. The neonIN network currently includes 30 NNUs. For the purposes of this project all centres that wish to participate in neoAMRO will have access to the electronic data collection tool or web based database and will capture anonymised data regarding invasive episodes of infection.

For the purposes of the neoAMRO study, information on the baby's status at 28 days after the positive culture will be collected (alive / died / not known). If the baby is alive, then this baby becomes eligible as a control. However, if the baby has died, then further details will be sought including the date of death and whether the infection was believed to be associated with the baby's death. Babies with positive cultures but who have died before receiving 5 days of appropriate antimicrobial therapy (currently a component of the surveillance case definition), will also be captured prospectively.

Thus, the following data will be collected as part of the neoAMRO study:

- outcome at 28 days (alive / died / not known)
- date of death
- cause of death (if association with infection)
- antibiotics: name / start date / dose / frequency / stop date
- whether antibiotic regime was changed during therapy
- reason for change in antibiotic regime
- new antibiotics: name / start date / dose / frequency / stop date

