8.6 Data protection and patient confidentiality

All data should be handled in accordance with the Data Protection Act 2018 (UK implementation of the EU General Data Protection Regulation (GDPR)).

The participant's trial Identification Number (ID) only, will be used for identification. The Subject ID log can be used to cross reference participant's identifiable information and will be stored securely at participating sites.

1. Describe the nature of the processing:

A member of the neonatal team at each centre will be responsible for data collection and data input. As infection cases arise, they will be entered onto an electronic data collection tool or web based database. The central database will be anonymised with subjects identified only by neonIN study number, SEND/BADGER number and date of birth. Once age at infection has been calculated the DOB will be removed from the database. Each participating unit will hold its own secure database in order to link the infants' identifying data with study numbers. All data will be stored in compliance with the Data Protection Act.

2. Describe the scope of the processing:

Routine data collected: contributing hospital, DOB (for calculation of age at infection), gender, birth weight, gestation, ward type, date blood culture taken, pathogens isolates, whether the baby received

antibiotics 48 hrs before the culture was taken, whether the mother received antibiotics in the week before delivery, presence of intravenous or arterial lines catheters at time the culture sample was taken, clinical conditions associated with the infection, results of positive cultures including antibiogram, country of the participating unit, date of admission to the neonatal unit, number allocated to the baby on the SEND/Badger database, denominator data from each participating unit to demonstrate the unit activity (number of live births, number of admissions, patient days in NNU, central line days).

The following data to be collected in addition to the neonIN data, as part of the neoAMRO study : outcome at 28 days (alive / died / not known), date of death, cause of death (if association with infection), antibiotics: name / start date / dose / frequency / stop date, whether antibiotic regime was changed during therapy, reason for change in antibiotic regime, new antibiotics: name / start date / dose / frequency / stop date.

The data will be kept for 5 years post study termination/end.

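### Sections 5.3 and 8.6 list outcome, antibiogram and antibiotic data for every baby, but section 7.2.1 compares deaths with only two matched survivors each; reconcile them and, if the data exist, use all eligible survivors

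*Protocol*

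**What the plan says.** Section 7.2.1 expects up to 800 babies with invasive infection, about half due to coagulase-negative staphylococci (CoNS), and around 50 deaths. It then makes the comparison "For all cases and for two controls per case (selected centrally, based on birth in same birthweight category and in same hospital". For these babies a standardised case report form captures, among other items, the antimicrobials given, relapses and length of stay. The power statement has the same basis: "With approximately 50 cases of death and 100 controls", to detect "susceptibility to empiric antibiotics of 80% among cases (or less) to 95% among controls", "with 95% significance and 80% power".

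The data collection sections are wider. Section 5.3 introduces its list with "Thus, the following data will be collected as part of the neoAMRO study". The list holds 28-day status and the name, dates, dose and frequency of antibiotics, including changes. The date of death and the link to infection are made conditional on death; the antibiotic fields carry no condition. Section 8.6 repeats the list, puts the antibiogram among the routine data, and says of entry: "As infection cases arise, they will be entered onto an electronic data collection tool or web based database". In that sentence a case is an infection episode, not a death.

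**The concern.** The exposure of interest is whether the empiric antibiotic matched the susceptibility of the isolate. It is built from the antibiotic fields and the antibiogram, and the outcome is 28-day status. On the plain text of sections 5.3 and 8.6, all three are listed for the whole cohort.

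Sampling controls saves effort when the exposure has still to be collected for each control. If it is already recorded, a fixed 2:1 ratio sets aside information without saving collection, and the protocol gives no reason for it.

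Two things are at stake. One is precision in a comparison where deaths are few and cannot be increased. The other is the absolute 28-day mortality with and without mismatch. That is the kind of figure that motivates the study in section 1, and the full cohort gives it directly. Section 7.2.1, however, reads as if the antimicrobial data come from a form completed only for the sampled babies. The sections therefore disagree on whether the data exist for the other survivors.

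**Working it through.** **Inputs, all from section 7.2.1:** 50 deaths; 100 controls; cohort of up to 800; about 50% CoNS; susceptibility 80% in cases (p1) and 95% in controls (p2); 5% level, taken as two-sided because the protocol does not state sidedness.

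**Survivors not sampled**
- Whole cohort: 800 − 50 − 100 = 650.
- Non-CoNS only, assuming that all deaths and all sampled controls are non-CoNS: 400 − 50 − 100 = 250.
- Both are upper figures, because 800 is a maximum and section 5.3 allows 28-day status to be not known.

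**Formula** (pooled-variance comparison of two proportions, unmatched):

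power = Φ{ [ |p1 − p2| − 1.96·√( p̄(1 − p̄)(1/n1 + 1/n2) ) ] / √( p1(1 − p1)/n1 + p2(1 − p2)/n2 ) }, with p̄ = (n1·p1 + n2·p2)/(n1 + n2).

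**The plan's own figure, 50 and 100**
- p̄ = 135/150 = 0.90.
- 1.96·√(0.09 × 0.03) = 0.10184.
- √(0.0032 + 0.000475) = 0.06062.
- (0.15 − 0.10184)/0.06062 = 0.794, giving **78.7%**. The stated 80% is reproduced to within 2 points.

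**Non-CoNS survivors, 50 and 350**
- p̄ = 372.5/400 = 0.93125.
- 1.96·√(0.06402 × 0.022857) = 0.07498.
- √(0.0032 + 0.000136) = 0.05776.
- (0.15 − 0.07498)/0.05776 = 1.299, giving **90.3%**.

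**All survivors, 50 and 750**
- p̄ = 752.5/800 = 0.940625.
- 1.96·√(0.05585 × 0.021333) = 0.06765.
- √(0.0032 + 0.000063) = 0.05713.
- (0.15 − 0.06765)/0.05713 = 1.441, giving **92.5%**.

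**Ceiling.** With 50 deaths and unlimited controls the same formula gives about 94.3%, so the deaths set the limit.

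**Dependence on the test**

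| Test | 50 v 100 | 50 v 350 | 50 v 750 |
|---|---|---|---|
| Pooled formula | 78.7% | 90.3% | 92.5% |
| Chi-square, exact enumeration | 81.0% | 91.8% | 93.7% |
| Continuity-corrected chi-square | 71.4% | 87.5% | 90.4% |
| Unpooled Wald | 69.6% | 73.8% | 74.7% |

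The gain from using all survivors is about 14 points with the pooled formula, 13 with the exact chi-square, 19 with the continuity correction and 5 with the unpooled Wald test.

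**Detectable difference.** Against 95% in controls and at 80% power (pooled formula), the susceptibility in cases that can be detected moves from 79.6% with 100 controls to 83.9% with 750.

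**Effect of hospital.** Section 5.3 puts the network at 30 units. On average that is 50/30 ≈ 1.7 deaths and 750/30 = 25 survivors per unit, so some units may well have no death. Survivors there contribute nothing to an analysis conditional on hospital and little to other hospital-adjusted models. The protocol gives no deaths by unit, so this loss cannot be computed. The planned 78.7% is also an unmatched figure.

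**The case against.** The strongest reply is that section 7.2.1, read plainly, uses sampling to decide who gets the case report form. A surviving baby only becomes eligible as a control (sections 5.2 and 5.3), which implies selection, and relapses and length of stay appear nowhere else. On that reading no antibiotic data exist for the other survivors. This stands as one of two readings. Sections 5.3 and 8.6 support the other, so the point has to be conditional.

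A reader might draw four stronger inferences that the documents do not support:

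- **That data on 650 survivors are discarded.** This takes as settled that the data exist. It also needs the maximum cohort, every outcome known, and CoNS survivors as useful comparators; without CoNS about 250 remain.
- **That the study is underpowered or loses most of its power.** The plan delivers about the power it states. The 92.5% is not the power of a hospital-adjusted analysis.
- **That every analysis is confined to two survivors per death.** The logistic regressions at the end of section 7.2.1 are not expressly limited to the 150 babies, and the primary aims are descriptive.
- **That absolute mortality by mismatch is beyond a 1:2 sample.** If 28-day status is known for the cohort, the sampling fractions are known and weighting can recover it, though less precisely.

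Matching on hospital and birthweight category is also a recognised control of confounding. If antibiotic data do have to be collected specially, a higher ratio means more forms on funding of £4,000, and enough survivors of the same hospital and birthweight category may not exist. That is a trade-off for the investigators and is not asked for here.

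**Conclusion.** The point holds in two parts. Without condition, section 7.2.1 and sections 5.3 and 8.6 do not agree on which babies have antibiotic data, and must be reconciled. Conditionally, if the fields are completed for every baby, restricting the comparison to two survivors per death gives up precision for no saving in collecting the exposure.

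The size is moderate: from about 79% to at most about 90% to 93% on the unmatched pooled formula, and less after accounting for hospital. This rests on 50 deaths, 80% versus 95%, a two-sided 5% test, a cohort near 800 with known outcomes and, for the lower figure, all deaths being non-CoNS. It concerns the secondary aim only and does not show that the stated power is wrong.

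**What to change.** 1. State in sections 5.3, 7.2.1 and 8.6, in the same terms, whether the antibiotic fields are completed for every baby entered or only for deaths and selected controls.
2. If for every baby, change section 7.2.1 so that the controls are all eligible survivors with known 28-day status. Analyse by a logistic regression that accounts for hospital (for example by conditioning on it) and adjusts for birthweight and organism group. Name this as the analysis set for the regressions.
3. In that case also report absolute 28-day mortality by empiric-antibiotic mismatch from the full cohort, with the number of babies of unknown status.
4. If only for the sampled babies, say so in sections 5.3 and 8.6 and give the reason for two controls per death.

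Under step 2 the cost is wording and slightly more analysis, with no extra patients or forms. The drawback is reliance on model adjustment instead of matching. Relapses and length of stay, named only in section 7.2.1, may stay limited to the sampled babies.

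### Section 7.2.1 compares deaths with 28-day survivors on post-culture items that death cuts short in cases only; the powered empiric-therapy contrast is not affected

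*Protocol*

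**What the plan says.** Protocol 7.2.1 defines the comparison: "All babies who have died within 28 days of a positive culture will then be compared with babies who have survived at 28 days". For every case and two controls per case, "this will be performed through collection of anonymised data including birth gestation, birth weight and age at infection", and the same list continues with "antimicrobials administered for that infection episode (and if changed), relapses, length of stay and attributable mortality at 10 days". Controls are "selected centrally, based on birth in same birthweight category and in same hospital"; time at risk is not a matching factor. The remaining risk factors go to univariate and multivariable logistic regression.

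Protocol 5.3 makes survival to day 28 the condition for being a control: "If the baby is alive, then this baby becomes eligible as a control". It collects start and stop dates for the first and later antibiotics, and "whether antibiotic regime was changed during therapy".

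Protocol 4.2 tests whether deaths are due to inappropriate antibiotic management, by comparing how appropriate, how well dosed and how prompt the antibiotics were. It gives no time window for these measures.

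The one quantified contrast in 7.2.1 is narrower: "susceptibility to empiric antibiotics of 80% among cases (or less) to 95% among controls", an exposure set when treatment begins.

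**The concern.** A control is by definition alive for the whole 28 days after the culture. A case is observed only until death, which may come within days. A regimen change, a later antibiotic or a relapse can be recorded only while the baby is alive. If these are tabulated as recorded, survivors show more of them simply because they had longer to do so. This is immortal-time bias. For length of stay the more exact term is truncation by death, because the outcome itself ends the measurement. Ten-day attributable mortality is an outcome that no 28-day survivor can have, so it cannot serve as a case-versus-control factor.

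The secondary hypothesis is at stake. If appropriateness or timeliness is scored over the whole episode, babies who lived long enough to have treatment corrected look better managed, whether or not correction affects survival.

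**Working it through.** **1. The plan's own figure.** Inputs from 7.2.1: "With approximately 50 cases of death and 100 controls", 80% v 95% susceptible, 5% significance (two-sided assumed).

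- Pooled proportion: (50 × 0.80 + 100 × 0.95) / 150 = 0.90.
- Null standard error: √(0.90 × 0.10 × (1/50 + 1/100)) = 0.0520.
- Alternative standard error: √(0.80 × 0.20/50 + 0.95 × 0.05/100) = 0.0606.
- Power: Φ((0.15 − 1.96 × 0.0520) / 0.0606) = 78.7%, against 80% stated.

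The figure reproduces. The exposure is fixed when treatment starts, so limiting the analysis to such exposures leaves this power unchanged.

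**2. Regimen change with no treatment effect.** The documents give neither death times nor change times, so these are assumptions: 40% of survivors change regimen, at a time E uniform on days 1 to 5; death time T in cases is exponential, truncated at 28 days, and independent of E. The proportion of cases with a recorded change is 0.40 × P(E < T). For scale 3 days, P(E < T) ≈ (3/4)(e^(−1/3) − e^(−5/3)) = 0.396, giving 0.158. The odds ratio is (0.158/0.842) / (0.40/0.60) = 0.28. The other rows come from simulation of the same model.

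| Scale of T (days) | Median death day | Change recorded, cases | Controls | Spurious OR | False significance, 50 v 100 |
|---|---|---|---|---|---|
| 3 | 2.1 | 15.8% | 40% | 0.28 | 88% |
| 5 | 3.4 | 22.5% | 40% | 0.44 | 57% |
| 10 | 6.3 | 29.2% | 40% | 0.62 | 25% |
| 30 | 10.9 | 33.8% | 40% | 0.77 | 11% |

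**3. Relapse with no effect.** Assume relapse in 10% of survivors, uniform on days 10 to 28. Over the same death times, 0.1% to 2.4% of cases have a recorded relapse, a spurious odds ratio of 0.01 to 0.22.

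**4. Direction for the hypothesis.** Assume 15% initial mismatch in both groups, correction at 72 hours in every mismatched baby still alive, no other changes, and 20% to 60% of cases dead before 72 hours.

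- *Never appropriately treated:* cases 0.15 × 0.20 = 3% to 0.15 × 0.60 = 9%; controls 0%. This is biased towards the hypothesis. In 50 cases it is 1.5 to 4.5 babies. At the low end, 2/50 v 0/100 gives Fisher p = (50 × 49)/(150 × 149) = 0.11.
- *Regimen change as a marker of mismatch:* cases 0.15 × 0.80 = 12% down to 0.15 × 0.40 = 6%; controls 15%. The odds ratio is (0.12/0.88)/(0.15/0.85) = 0.77 down to (0.06/0.94)/(0.15/0.85) = 0.36. Cases look less mismatched than controls, which is biased against the hypothesis.

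The same truncation therefore pushes the conclusion either way, depending on how the variable is built.

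**The case against.** The strongest reply is that 7.2.1 lists what the case report form records, not what enters the model. The list mixes baseline items, a matching factor, treatment and an outcome, so it cannot be a list of risk factors. Nowhere does the protocol name relapse, length of stay or 10-day mortality as a covariate. Relapse and stay are also absent from the data lists in 5.3 and 8.6, and 10-day mortality has its own stated purpose of attributing death to infection. Exposure windows are commonly left to a statistical analysis plan, and the dates needed to apply one are collected.

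Much of this stands. A reader might infer that the protocol plans to test relapse or stay as predictors of death; it does not say so. A reader might also infer that the whole case-control comparison is invalid; it is not, because the initial regimen, birth weight, gestation and age at infection are not affected by survival after the culture. Nor do the documents support the view that the bias always favours the hypothesis, as step 4 of the working shows.

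One thing is left. The sentence in 7.2.1 says the comparison itself is carried out through these data, and 4.2 puts timeliness and appropriateness into it with no common time at risk. That is the protocol's own wording of the comparison, not a detail left open, and an analysis plan could repair it only by narrowing what 7.2.1 says.

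**Conclusion.** The point holds for the post-culture items. Compared as recorded, regimen change, relapse, length of stay and any whole-episode score of appropriateness or timeliness differ between deaths and 28-day survivors without any treatment effect, and 10-day attributable mortality has no meaning as a case-versus-control factor. Under the assumed timings the spurious odds ratio is 0.28 to 0.77 for regimen change and 0.01 to 0.22 for relapse. These figures illustrate the mechanism and do not predict this study's result. Fewer recorded changes and relapses among cases is a consequence of the design; the size depends on death and change times that the documents do not give. Whether the error helps or hurts the hypothesis depends on the variable. The headline contrast and its power stand.

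**What to change.** In 7.2.1, separate the items recorded from the factors compared:

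- **Risk-factor comparison:** use exposures fixed at or near the culture, namely empiric regimen against isolate susceptibility, initial dose, and baseline factors.
- **Timeliness and regimen change:** count each control's exposure only up to its matched case's time from culture to death. The matched sets must be kept in the analysis for this.
- **Relapse and length of stay:** describe within survivors.
- **Ten-day attributable mortality:** describe in the cohort or within cases.

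The cost is a few sentences, slightly more analysis code and fewer variables in the comparison. Antibiotic start and stop dates and date of death (5.3) and culture date (8.6) are already collected. They are dates rather than clock times, so truncation works to the day and is coarse for the earliest deaths. The stated power does not change.
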